STUDY PROTOCOL

Overweight and obesity are public health problems worldwide and in Mexico, both related to the increase in weight and body fat that are risk factors for the development of chronic degenerative diseases such as type 2 diabetes mellitus (DM2) and cardiovascular diseases (CVD). The World Health Organization (WHO) defines obesity as the excessive accumulation of fat that can harm health and is diagnosed when the Body Mass Index (BMI) is greater than or equal to 30 kg/m².

In Mexico, according to figures from the National Health and Nutrition Survey (ENSANUT), at the national level, 75.2% of adults are overweight or obese (39.1% overweight and 36.1% obese), with respect to chronic degenerative diseases there is a prevalence of 10.3 % for diabetes, 18.4% for hypertension and it has been reported that 19.5% of the population has elevated cholesterol and triglycerides.

Correct diet and a healthy lifestyle are factors that help to avoid overweight and obesity; However, the current diet of the adult Mexican population is not adequate, because there is low consumption of the recommended food groups. Fruits and vegetables are healthy foods that less than 50% of the country's population consume daily. Regarding other recommended food groups, eggs are consumed by 29.9% of the population, dairy products by 47%. and unprocessed meats by 64.6%. Which is inadequate, due to the vitamins and minerals that these food groups provide.

Vitamins are considered micronutrients and they play an essential role in metabolism. Vitamins are classified according to their nature as fat-soluble or water-soluble. Water-soluble vitamins include vitamin B1, B1, B2, B3, B5, B6, B7, B9, B12 and C, while fat-soluble vitamins are vitamins A, E, D and K. Vitamin K (VK) has two main structural forms, which are phylloquinone (K1) which is found naturally in plant foods, mainly in green leafy vegetables, and menaquinone (K2) which is produced in the intestine and is found in some fermented foods. VK acts as a cofactor for the carboxylation of glutamic acid residues in proteins involved in blood coagulation and bone metabolism, facilitating calcium uptake through the carboxylation of the protein osteocalcin. This last protein, osteocalcin in its carboxylated form (OCc), serves as an indicator of the level of VK, the more OCc exists in the blood it is considered that there is a good level of VK, the osteocalcin that is not carboxylated thanks to the VK, circulates in the blood and is known as undercarboxylated osteocalcin (OCuc). VK requirements are 120mcg/day for men and 90mcg/day for women; Although VK is fat-soluble, the body stores small amounts that are quickly depleted without regular daily ingestion.

Various studies mention that the high intake of VK has positive effects on insulin sensitivity and cardiovascular risk; likewise, VK deficiency is negatively associated with the same factors. Yoshida et al. suggest that the increase of VK intake through diet can reduce the progression of insulin resistance. The mechanism through which VK improves insulin sensitivity is unknown. In animals, OCuc has been shown to stimulate beta cell proliferation and increase insulin secretion; However, Yoshida et al. found that in subjects receiving VK supplements the OCuc levels were lower and the insulin resistance was reduced, compared to the control group without supplements. This suggests

that VK may intervene in glucose metabolism through other mechanisms not fully described, such as suppression of inflammation. Also, it has been reported that VK improves insulin sensitivity in peripheral tissues without intervening in insulin resistance. Rasekhi et al. analyzed the effects of administering 100 mcg of VK through supplements on glucose metabolism in premenopausal prediabetic women. They found that in the group with VK ingestion, OCc levels increased and OCuc levels decreased and insulin sensitivity showed to improve. There were no alterations in total osteocalcin or in the HOMA-IR index. Which suggests that VK could improve insulin action in peripheral tissues.

Dietary supplementation with VK has been associated with an increase in insulin sensitivity and improvement in glycemic status. Yoshida et al. studied vitamin K supplementation for 36 months in men and women, administering 500 mcg/day of VK, 600 mg of calcium in the form of calcium carbonate and 10 mcg of vitamin D. They found that VK in supplements produces a protective effect on the progression of insulin resistance; Hussein et al. showed in animal models with type 2 diabetes the effect on glycemic status after the administration of VK supplements for 8 weeks. Those rats type showed a decrease in fasting serum glucose, HbA1c and insulin resistance, in addition to improving insulin sensitivity. When comparing the control group with the diabetes group without supplements, total OC levels were lower in the diabetes group; however, there was a dose-dependent relationship and the group with VK supplements showed to increase OC levels. In Mexico, the numbers of obesity and overweight increase considerably, the dietary factor has high relevance in the generation of these conditions, currently, studies on vitamin supplementation have been carried out, however in our country there is no evidence of the effect of dietary intervention with a high intake of VK on people with metabolic disorders such as overweight and obesity, so carrying out this study may contribute to explaining the participation of a high intake of VK on the improvement and prevention of overweight and obesity, in addition to evaluating the possibility to improve metabolic and bone health from a diet calculated in the Mexican population.

Work hypothesis

Dietary intervention with a high intake of vitamin K of 500mcg for 6 weeks, increases VK and OC serum levels, decreases insulin and leptin levels and reduces cardiovascular risk in young adults, with and without overweight or obesity.

Aims

General aim

To evaluate the effect of dietary intervention with a high intake of vitamin K of 500mcg on serum levels of vitamin K, insulin, osteocalcin, leptin and on cardiovascular risk in young adults with and without overweight or obesity.

Specific aims

- Design a dietary intervention with a 500mcg of vitamin K

- Compare serum levels of vitamin K, insulin, osteocalcin, leptin and cardiovascular risk markers before and after the intervention with high vitamin K intake in subjects with and without overweight or obesity.
- Analyze the relation between vitamin K serum levels and body composition characteristics, metabolic markers and insulin, osteocalcin, leptin and cardiovascular risk percentage in subjects with and without overweight or obesity.

Ethical considerations:

The study will adhere to the regulations established by the Mexican government in the regulations of the general health law regarding health research.

It will be carried out in accordance with the ethical standards and principles for medical research on human subjects established in the Declaration of Helsinki in Helsinki, Finland in 1964, updated in 2008 in Seoul, South Korea.

The subjects who will participate in the study will voluntarily sign the informed consent letter. The project aims to contribute to the study of metabolic diseases in adults and young people with the aim of finding strategies for prevention or use as early dietary treatment and the consideration of foods with a high supply of vitamin K. The participants in the study will be assigned an identification key to guarantee the reliability of their clinical data. If they decide to withdraw from the study, the clinical history and biological samples associated with the individual will be deleted. All individuals who participate in the study will benefit from obtaining and explaining their clinical data, information about the cardiovascular risk they have at the time of the intervention and after it, in addition to being provided with nutritional care and intervention by professionals of nutrition, all this without costs.

Biosafety aspects:

This is an investigation with minimal risk, the laboratory has the necessary infrastructure and materials for the management of RPBI according to the Official Mexican STANDARD NOM-087-ECOL-SSA1-2002, Environmental protection - Environmental health - Biological hazardous waste - infectious

- Classification and handling specifications. Waste from the use of reagents for ELISA and wet chemistry will be discarded according to the manufacturer's criteria. The reagents will be stored according to what is stipulated in the manufacturer's sheets and according to the provisions of NOM-054-SEMARNAT1993 and NOM-052-SEMARNAT-2005, no toxic, radioactive or explosive reagents will be worked with. The implementation of the project will be subject to what is described in the General Health Law on health research, DOF reform 04-02-2014 Art. 13 to 17. The main researcher has been trained by the CUCS Biosafety Committee.

METHODOLOGY

Technical methods and instruments for collection, recording, processing and analysis:

- Peripheral blood samples will be taken by venipuncture using the Vacutainer® system.
- The serum variables of glucose, triglycerides and lipids will be obtained by means of colorimetric enzymatic reagents. Vitamin K and insulin will be obtained through ELISA Kits.
- Anthropometric measurements will be carried out using a TANITA brand bioimpedance scale, SECA brand measuring tape and Slim Guide brand plicometers. All measurements will be taken according to ISAK.
- Blood pressure will be measured with an OMRON brand baumanometer.
- Patient data will be recorded in a log and in an Excel database. For the statistical processing of the data, the Excel, SPSS Statistics version 20.0 and GraphPad Prism 8 programs will be used.

Research organization:

The study will be carried out at the University of Guadalajara, Department of Molecular Biology and Genomics, Biochemistry Research Laboratory of the University Center for Health Sciences.

1. Once the patients are included, an initial evaluation will be carried out that consists of:

- Evaluation of nutritional status: Dietary analysis by 24-hour recall, anthropometric analysis (with bioimpedance, measurement of skin folds and circumferences), clinical history.
- Blood sample collection: determination of glucose and serum lipids, vitamin K, insulin and osteocalcin.
- Blood pressure measurement.
- Dietary intervention: Explanation of the study and dietary indications.

2. Dietary intervention with a high intake of vitamin K for 6 weeks

- Weekly monitoring of dietary adherence
- Nutritional advice: resolve doubts, evaluation of dietary adherence.

3. Final evaluation

- Evaluation of nutritional status: anthropometric analysis.
- Blood sample collection: determination of glucose and serum lipids, vitamin K, insulin, osteocalcin and leptin.
- Blood pressure measurement.
- Final evaluation of dietary adherence through a survey.

4. Data analysis, statistics.

5. Results report

Statistical analysis:

The statistical analysis will be carried out with the statistical package SPSS version 20, GraphPad Prism 9 and Excel 2011. Initially, the Kolmogorov-Smirnov test will be applied to all variables to verify if they followed a normal distribution model. Those variables that followed a normal distribution will be analyzed using parametric tests; Otherwise, non-parametric statistics will be applied.

Descriptive Analysis: mean, standard deviation, standard error of the mean, minimum, maximum and range. Inferential Analysis: Parametric tests (Student's t for independent samples), non-parametric tests (Kruskal Wallis). Comparative analysis: Chi square. Correlations: Spearman for non-parametric and Pearson for parametric tests.

Probability values less than 0.05 will be considered significant.

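### The plan claims a fall in leptin but lists leptin only at the final visit, and it claims an effect of the diet from a before-after comparison with no concurrent control described

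*Combined protocol and SAP*

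**What the plan says.** All references are to the combined protocol and SAP.

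- **Work hypothesis**, which states: "Dietary intervention with a high intake of vitamin K of 500mcg for 6 weeks, increases VK and OC serum levels, decreases insulin and leptin levels". The sentence goes on to claim a reduction in cardiovascular risk.
- **General aim:** "To evaluate the effect of dietary intervention with a high intake of vitamin K of 500mcg on serum levels of vitamin K, insulin", continuing with osteocalcin, leptin and cardiovascular risk.
- **Specific aims, second item:** "Compare serum levels of vitamin K, insulin, osteocalcin, leptin and cardiovascular risk markers before and after the intervention with high vitamin K intake". This covers both weight groups.
- **Specific aims, third item:** "Analyze the relation between vitamin K serum levels and body composition characteristics, metabolic markers and insulin, osteocalcin, leptin and cardiovascular risk percentage". The visit or visits to be used are not stated.
- **Research organization, item 1 (initial evaluation), blood sample:** "determination of glucose and serum lipids, vitamin K, insulin and osteocalcin". Leptin is not listed.
- **Research organization, item 2:** one six-week diet high in vitamin K, with weekly adherence monitoring and "Nutritional advice: resolve doubts, evaluation of dietary adherence".
- **Research organization, item 3 (final evaluation), blood sample:** the same analytes as at baseline, plus leptin.
- **Background:** the rationale says the study "may contribute to explaining the participation of a high intake of VK on the improvement and prevention of overweight and obesity". One cited supplement study is described as finding that "the insulin resistance was reduced, compared to the control group without supplements".

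The methodology and analysis sections describe no usual-diet, delayed-start or other untreated group. Control groups are mentioned only in connection with cited studies.

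**The concern.** The hypothesis makes directional claims about what the diet does, and two features of the plan stop it from supporting them.

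The first is a conflict over leptin. A change needs two measurements and the schedule lists one. If the baseline panel is followed as written, baseline leptin will not be assayed. It may not be recoverable later, since the documents set out no plan to keep serum for that purpose.

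The second is the step from change to effect. With one sequence for everyone, a fall in insulin or in a risk marker shows that the marker fell during six weeks. It does not show that the diet caused the fall, and still less that vitamin K did. The hypothesis and general aim are worded as effects and nothing in the analysis section limits that wording, so a significant before-after difference could be taken as confirming the hypothesis.

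**Working it through.** The documents give no sample size, effect size, standard deviation or power, so there is no figure of the plan's own to reproduce. The check sets the sections side by side.

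**Step 1. Leptin schedule.** Inputs: the four serum outcomes named in the second specific aim, and the blood panels in Research organization items 1 and 3.

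| Serum outcome | Baseline panel | Final panel | Visits listed | Change computable |
|---|---|---|---|---|
| Vitamin K | yes | yes | 2 of 2 | yes |
| Insulin | yes | yes | 2 of 2 | yes |
| Osteocalcin | yes | yes | 2 of 2 | yes |
| Leptin | no | yes | 1 of 2 | no |

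Change = final value − baseline value. For leptin the second term is not on the schedule, so 1 of the 4 serum outcomes has no before-after pair.

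**Step 2. What a before-after change contains.** For any marker measured twice, write

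mean change = K + D + A + T,

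where K is the contribution of vitamin K, D that of other components of the diet, A that of weekly monitoring and nutritional advice, and T change over time that would have occurred anyway. The design observes one quantity, the sum.

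- The effect of the intervention as a whole is K + D + A. Isolating it requires T, which a concurrent group off the intervention would estimate. None is described.
- The effect of vitamin K is K alone. Isolating it also requires D and A, and no group receives those without the high vitamin K intake.

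**Step 3. Can one weight group act as control for the other?** Let E = K + D + A, with subscripts 1 and 2 for the two weight groups. Both receive the diet, so

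difference in change = (E₁ + T₁) − (E₂ + T₂) = (E₁ − E₂) + (T₁ − T₂).

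If the two groups respond equally and drift equally, this is zero whatever the size of E. The contrast concerns whether the groups differ in response, not whether the diet works. The weight groups are strata, not treated and untreated arms.

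**Step 4. Does the third specific aim fill the gap?** It relates serum vitamin K to the markers. With final or change values, a participant who adheres closely to the whole diet may have both higher vitamin K and a better marker, through D rather than K. With baseline values that route is closed, because nobody has yet followed the study diet, but a baseline correlation says nothing about what the diet does. Neither version replaces a control.

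**The case against.** **Leptin is probably a drafting slip.** The second specific aim states the before-after leptin comparison outright, and the document's lists are incomplete elsewhere: the technical methods name ELISA kits only for vitamin K and insulin, yet osteocalcin is in both panels. This is fair. A reader might infer that the leptin hypothesis is untestable in this study. The documents support only that it cannot be tested on the schedule as written. The sections still conflict and must be reconciled.

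**Uncontrolled before-after studies are legitimate.** Agreed. The point asks for a claim that matches the design, not for a control arm.

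**The hypothesis names the diet, not vitamin K alone.** Correct. The vitamin-K-specific gap rests largely on a hedged sentence in the background, so it is the weaker half. The gap for the diet as a whole remains, because change over time is not removed.

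**A control may be described on a removed page.** Title and consent pages are not available, so the finding is that none is described in the text available. The methodology is present, however, and gives a single sequence.

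**Stronger readings to avoid.** A reader might add regression to the mean as an explanation for any fall. That needs selection on high or noisy baseline values of the outcome. The documents define the groups by weight status, include people without excess weight, and describe no selection on insulin, leptin or cardiovascular risk. A reader might also want a probability of a false positive conclusion. Any such figure would need an assumed sample size and drift, neither of which the documents give. Finally, one might say that the sponsor will report a fall as proof. The documents promise only a report of results, so the risk lies in the wording of the hypothesis and aims rather than in any stated reporting intention.

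**Conclusion.** The point holds in two parts.

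(a) The hypothesis and the second specific aim require a leptin change that the written visit schedule cannot supply. This needs no assumption beyond reading the two blood panels as they stand.

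(b) The hypothesis and general aim state an effect of the six-week diet, while the described design yields only change during it. That change cannot be separated from change over time, nor assigned to vitamin K apart from the other diet components, monitoring and advice. This rests on no concurrent control being described in the available text.

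The only size the documents support is the visit count for leptin. The extent of any misattribution in (b) cannot be quantified from them. Both parts should be corrected. The leptin conflict is the more concrete and the more urgent, because it has to be settled before baseline samples are processed.

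**What to change.** 1. **Leptin.** Add leptin to the baseline panel in Research organization, item 1, using the blood sample already planned. Cost: one more assay per participant. If this is not done, remove leptin change from the Work hypothesis, the General aim and the second specific aim, and keep leptin only as a final-visit correlation under the third. Cost: loss of the leptin-change claim.

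2. **Wording of the claim.** In the Work hypothesis, the General aim and the reported conclusion, replace effect language with change during the six-week high-vitamin-K dietary intervention.

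3. **Statement in the Statistical analysis section.** Add, for example: *There is no control group, so changes are not attributed to the intervention or to vitamin K specifically. Correlations of final or change values with serum vitamin K are descriptive.*

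Items 2 and 3 are text changes only. Their downside is a more modest claim.

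### Does the hypothesis need amending because it predicts a rise in osteocalcin without saying which form is measured?

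*Combined protocol and SAP*

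**What the plan says.** The Work hypothesis states that the intervention "increases VK and OC serum levels". The abbreviation OC is not expanded there. The General aim, the second and third Specific aims, and the blood panels in items 1 and 3 of Research organization speak only of osteocalcin. The list of technical methods under Methodology assigns colorimetric enzymatic reagents to glucose and lipids and ELISA kits to vitamin K and insulin. It assigns nothing to osteocalcin, or to leptin.

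The introduction does separate the forms. It says that "osteocalcin in its carboxylated form (OCc), serves as an indicator of the level of VK", and it gives the undercarboxylated form its own abbreviation, OCuc. One human study, "administering 100 mcg of VK through supplements on glucose metabolism in premenopausal prediabetic women", is reported for all three measures: "OCc levels increased and OCuc levels decreased and insulin sensitivity showed to improve", and "There were no alterations in total osteocalcin or in the HOMA-IR index". In the rat study "total OC levels were lower in the diabetes group", while "the group with VK supplements showed to increase OC levels".

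**The concern.** The introduction's evidence points in three directions depending on the form: up for OCc, down for OCuc, flat for total. A prediction that osteocalcin rises, with no form attached, could therefore be supported, contradicted or null according to which kit is bought.

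If total osteocalcin were assayed and behaved as in the three-form human study, that part of the hypothesis would come out null even if vitamin K acted as the introduction describes. The planned correlation between serum vitamin K and osteocalcin would also be run on a form that the introduction does not call the indicator. Once serum has been used on one kit, the choice may be hard to reverse. There is also a textual argument that total is meant: the only other bare use of OC comes just after a mention of total OC, in the rat study.

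**Working it through.** No sample size, standard deviation, effect size or power is given for osteocalcin, so there is no figure to reproduce. The check is textual, with two small pieces of arithmetic.

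1. **Count of mentions for this trial.** Work hypothesis 1 + General aim 1 + Specific aims 2 + initial panel 1 + final panel 1 = 6. Form named: 0 of 6. Assay named: none. The gap exists as described.

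2. **Does the bare term point to total?** The introduction tags OCc, OCuc and also total osteocalcin (in the three-form human study and in the rat study). Since all three are tagged when meant, the absence of a tag favours none of them. One rat-study sentence leans towards total. Against it, the introduction treats more OCc as a sign of good vitamin K status, and the hypothesis pairs vitamin K and OC as rising together. That pairing fits OCc at least as well.

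3. **Which forms fit a predicted rise?**

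| Form | Evidence cited in the introduction | Fits a predicted rise? |
|---|---|---|
| OCc | Up in the three-form human study; named as the vitamin K indicator | Yes |
| OCuc | Down in that study; lower than in unsupplemented controls in a second human report | No |
| Total | Unchanged in that study; OC rose with dose in rats | Possibly |

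The stated direction narrows the sensible readings to OCc or total.

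4. **Is total known to be unresponsive here?** The null human result was at 100 mcg by supplement in prediabetic women. This trial uses 500 mcg by diet in young adults, and 500 / 100 = 5 times the dose. The cited study "administering 500 mcg/day of VK" does not settle the matter, because its summary reports insulin resistance and gives no osteocalcin result.

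5. **Can a loss be sized?** Assume total = OCc + OCuc in the same units. If OCc changes by +a and OCuc by −k·a, total changes by (1 − k)·a: 1.0a at k = 0, 0.5a at k = 0.5, and 0 at k = 1. The documents give no value for k, so the possible dilution runs from none to complete. This shows how a total assay could mask a change; it is not evidence that it would.

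6. **Reach.** Serum vitamin K and osteocalcin are both in the initial and the final panel. Any ambiguity is confined to the osteocalcin before-after comparison and its correlations. Osteocalcin is one of several outcomes, and none is designated primary.

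**The case for a change.** The strongest contrary case does not depend on which form was intended. A hypothesis whose expected sign turns on an unstated assay is not fully specified, it leaves room to choose the form after results are seen, and naming the form would cost only a line of text. If OCc is meant, the plan says so nowhere for this trial.

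Part of this stands: the form is unwritten, and a reader cannot be certain of it from the text. Three things weaken the step from there to a required change. Each panel lists osteocalcin as a single item, and nothing in the plan proposes measuring several forms and selecting among them. The assay cannot be run without deciding what it measures, and the authors, who set out the forms and their different behaviour themselves, are well placed to decide it. A mandated ranking of the forms would also go beyond the documents. OCc has the indicator role, but OCuc is linked to insulin secretion in animals and insulin is an outcome here, while the stated interest in bone health and the rat data give a reason to look at total. The choice belongs to the investigators.

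**Conclusion.** The concern identifies a real omission but does not call for a change. No stated rule is shown to produce a wrong result. A misleading null would require both that a total assay is run and that total fails to respond under this diet, and the documents establish neither.

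The size of any harm cannot be calculated from what is given. This conclusion assumes that the investigators choose the kit with their own account of the three forms in mind, and that the form used is stated with the results. On that basis this is a missing detail that competent investigators fill in the ordinary course of the work.

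### Baseline vitamin K intake and status are not used to adjust or explain response, so a difference between the non-randomised weight groups could partly reflect unequal exposure

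*Combined protocol and SAP*

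**What the plan says.** - **Target.** The Work hypothesis describes the intervention as "Dietary intervention with a high intake of vitamin K of 500mcg for 6 weeks", and the first specific aim repeats the figure ("Design a dietary intervention with a 500mcg of vitamin K"). It is the same for all participants. Neither place says whether it is a total or an addition to the usual diet, and neither attaches a per-day basis.
- **Baseline measurement.** Research organization, item 1, lists "Evaluation of nutritional status: Dietary analysis by 24-hour recall" and "Blood sample collection: determination of glucose and serum lipids, vitamin K, insulin and osteocalcin". It does not say that the recall will be converted into vitamin K intake.
- **Final measurement.** Item 3 lists "Blood sample collection: determination of glucose and serum lipids, vitamin K, insulin, osteocalcin and leptin" and an adherence survey. No second recall is listed.
- **Aims.** The second specific aim compares the markers before and after the diet in people with and without overweight or obesity. The third relates serum vitamin K to body composition and the other markers, without giving a time point or saying whether levels or changes are meant.
- **Analysis.** The Statistical analysis section names "Parametric tests (Student's t for independent samples), non-parametric tests (Kruskal Wallis"), chi-square, and Pearson or Spearman correlations. It names no covariate, adjusted model or effect modifier.

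**The concern.** Both named tests for continuous outcomes compare independent groups. In a study with one diet, the natural groups are those with and without overweight or obesity. Those groups are not formed by randomisation, so they may differ at the start in how much vitamin K they eat and in their vitamin K status. Everyone then receives the same target. If starting points differ, the groups may undergo different changes in exposure, and an unadjusted comparison of response cannot separate that from an effect of adiposity.

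The protocol's own rationale makes a dietary difference plausible. The background says a correct diet helps to avoid overweight, places vitamin K1 mainly in green leafy vegetables, and says body stores run down quickly without regular intake.

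There is also a missed opportunity. With no comparison diet, a before/after change cannot by itself be attributed to vitamin K. Whether response follows starting vitamin K is one of the few internal checks available, and the data for it are largely scheduled already.

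**Working it through.** The plan gives no sample size, SD, effect size or intake distribution, so there is no figure of its own to reproduce. The check has two parts: what the listed analyses can do, and how large the problem could be under stated assumptions.

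**1. What the listed analyses can do**

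| Analysis named | Can it adjust a weight-group comparison for baseline intake or status? |
|---|---|
| Independent t test, Kruskal-Wallis | No |
| Chi-square | No |
| Pearson or Spearman correlation | No; two variables at a time |

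Baseline serum vitamin K does appear as the before value for the vitamin K outcome (second aim), and may enter the third-aim correlations. Baseline intake appears in no stated analysis.

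**2. Increment, if 500 mcg is a daily total**

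Increment = 500 − habitual intake. The background gives reference intakes: "VK requirements are 120mcg/day for men and 90mcg/day for women".
- Woman at the reference intake: 500 − 90 = 410 mcg.
- Man at the reference intake: 500 − 120 = 380 mcg. Ratio 410/380 = 1.08.
- Assumed wider range, 45 and 250 mcg: increments 455 and 250 mcg. Ratio 455/250 = 1.82.

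If 500 mcg is added to the usual diet, the increment in mcg is the same for everyone. Only starting status and the fold change then differ.

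**3. Spurious group difference as a share of the mean response**

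Let d be the gap in mean habitual intake between groups and m the overall mean, assumed 90 to 120 mcg/day. Again 500 mcg is taken as a daily total.
- Linear response: d/(500 − m). For d = 30: 30/410 = 7.3% to 30/380 = 7.9%. For d = 100: 24.4% to 26.3%.
- Logarithmic response: ln(hi/lo) divided by the mean of ln(500/lo) and ln(500/hi), with hi and lo = m ± d/2. For d = 30 and m = 90: ln(105/75) = 0.336; mean of ln(500/75) and ln(500/105) = 1.729; ratio 19.5%. At m = 120 it is 17.5%. For d = 100: 58% to 66%.

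**4. In SD units, and the chance of a false finding**

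Assume 1 SD of response per 400 mcg, linear. The spurious difference is d/400: 40/400 = 0.10 SD and 80/400 = 0.20 SD.

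With n per group and k = difference/√(2/n), the two-sided rejection rate at 0.05 is P(Z > 1.96 − k) + P(Z < −1.96 − k). The values of n are assumed.

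| Difference | n = 20 | n = 30 |
|---|---|---|
| 0.10 SD | k = 0.316: 6.2% | k = 0.387: 6.7% |
| 0.20 SD | k = 0.632: 9.7% | k = 0.775: 12.1% |

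The nominal rate is 5%.

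**5. What adjusting for the recall removes**

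If the recall has reliability r as a measure of habitual intake within groups, the bias left after adjustment is about (1 − r) times the original.
- r = 1: none left.
- r = 0.5: 0.05 SD (40 mcg gap) and 0.10 SD (80 mcg gap).
- r = 0.3: 0.07 and 0.14 SD.

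Simulation of 4,000 trials per setting (habitual-intake SD 60 mcg, 20 to 30 per group) agrees. Unadjusted bias was 0.10 and 0.19 SD. It fell to 0.06 and 0.09 SD at r = 0.5, and to 0.07 and 0.14 SD at r = 0.3.

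**The case against.** The strongest reply is that the plan never claims adiposity alters the response. The Work hypothesis predicts the same direction of change with and without overweight or obesity, and the second aim is before versus after. On this view an adjusted group comparison repairs a claim nobody makes. This stands in part: a weight-group difference is not a stated hypothesis. But both named tests for continuous outcomes compare groups and the aims split participants by weight, so such differences are likely to be reported and interpreted.

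Three stronger readings are tempting, and the documents do not support them.
- *Every participant receives a different increment.* In mcg this needs 500 to be a total. The wording leans that way but does not settle it.
- *Weight-group differences are confounded by intake.* This needs a gap in starting intake or status. The documents report no intake by weight; the figure on daily fruit and vegetable consumption describes the whole population.
- *Baseline serum vitamin K is unused.* It is the before value in the second aim and may enter the third. What is missing is its use as a covariate or modifier of response.

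Two further objections hold and shape the remedy. A model of change that omits a marker's own baseline lets regression to the mean into the vitamin K slope. And leptin, an outcome in the before/after aim, is absent from the initial blood list, so no baseline-adjusted leptin model can be fitted as scheduled.

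**Conclusion.** The gap is real and modest. As written, the plan cannot tell a weight-group difference in response from a difference in starting vitamin K, and it does not use scheduled measurements that would help. Whether this would mislead is unknown, because it depends on a gap between groups that the documents do not report.

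Under a linear response, with 500 mcg as a daily total, the assumed gaps of 40 to 80 mcg give about 0.10 to 0.20 SD and raise the false-positive rate from 5% to between 6% and 12% at 20 to 30 per group. A logarithmic response would make the distortion larger: up to about two-thirds of the mean response for a 100 mcg gap. The gaps, dose-response shape, SD scale, reliabilities and group sizes are all assumptions. The calculation also takes the target as fully achieved; with no final recall listed, achieved intake cannot be computed.

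This supports a secondary, exploratory analysis. It does not show that the planned unadjusted comparison is invalid.

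**What to change.** 1. Keep the unadjusted weight-group comparison. Beside it, as a pre-specified secondary analysis, fit for each marker measured at both visits a linear model of the final value on that marker's own baseline, weight group and baseline serum vitamin K. Add baseline vitamin K intake where the recall yields it, and state whether it will.
2. Report the vitamin K slopes as an exploratory check of whether response follows starting status.
3. For serum vitamin K itself, use the final value as outcome and its own baseline as covariate. Do not read that slope as response, since regression to the mean contributes to it.
4. Reconcile the blood lists in Research organization, items 1 and 3, with the before/after aim for leptin. Until then the model cannot cover leptin.
5. State whether 500 mcg is a total or an added intake, and over what period, so that the increment is defined.

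**Cost.** One extra model per marker, with no new visits. No new assays are needed for markers already listed at both visits. It uses a few degrees of freedom; with no sample size stated, the loss of precision cannot be judged. Adjustment is partial because a single recall is noisy. Because the groups are not randomised, baseline-adjusted and unadjusted results can legitimately differ, so both should be shown and labelled exploratory.
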